1.2.1. Randomization

One eye in each subject will be designated as the study eye. Following confirmation of eligibility on Day 1, subjects will be randomly assigned in a 1:1 ratio to either Yutiq 0.05 mg or sham injection through a central Interactive Voice Response System (IVRS). Randomization will be stratified based on whether the subject is receiving systemic treatment to control uveitis at the time of study entry.

2. Statistical Hypotheses

Not applicable.

2.1. Multiplicity Adjustment

Not applicable.

3. Analysis Sets

For the purposes of analysis, the following analysis populations are defined:

3.1. Intent-to-Treat Analysis Set

The Intent-to-Treat (ITT) analysis set will include all subjects who are randomized. Subject will be classified according to the assigned treatment. The ITT set will be used for analysis of efficacy, unless otherwise specified.

3.2. Safety Analysis Set

The Safety Analysis Set (SAS) will include all subjects who are randomized and received Yutiq 0.05 mg or sham injection. Subjects will be classified according to the actual treatment received. The SAS set will be used for the analysis of safety data.

4. Statistical Analyses

4.1. General Considerations

4.1.1. Data Summarization

The Sponsor decided to stop enrollment in early May 2022. Subjects who were randomized to Yutiq 0.05 mg will continue to be monitored on a modified-protocol schedule. The subjects who had been treated with sham injection were discontinued from the study. Consider the fact that the study was terminated early, no statistical hypothesis testing will be performed. All data summaries will be descriptive only, based on observed data.

Tabular data summaries for variables measured on a continuous scale will include descriptive statistics (n, mean, median, standard deviation, minimum, and maximum) by treatment group and visit.

For variables evaluated on a categorical scale, data summaries will include the number and percentage of subjects who provide each possible category, by treatment group and visit when applicable. The 95% confidence interval (CI) of the proportions will be constructed for each treatment group, as appropriate.

All study data will be presented in by-subject listings.

4.1.2. Definition of Baseline

Baseline measurements are those taken at Screening or prior to receiving study treatment on Day 1, whichever is the latest.

4.1.3. Analysis Visit Windows

There will not be visit date re-mapping for the data analyses. All analyses will be descriptive. Descriptive summary tables will be based on nominal visits.

- Efficacy endpoints labelled as Week 24 endpoint will use the assessments from Month 6 visit.
- Efficacy endpoints labelled as Week 52 endpoints will use the assessments of Month 12 visit.

4.1.4. Handling of Missing Data

In general, missing data will not be imputed, unless otherwise specified. For missing and partial dates imputation, refer to section 6.3.1.

4.1.5. Multicenter Considerations

Up to 40 investigative study centers will participate in the study. All centers will be in the United States. Data will be pooled for all study centers for data analysis, unless otherwise specified.

4.1.6. Adjustment for Covariates

Not applicable.

4.1.7. Multiple Comparisons and Multiplicity

Not applicable.

4.1.8. Statistical Software

All statistical summaries and analyses will be produced using SAS, Release 9.4 or higher.

4.2. Primary Efficacy Endpoint Analysis

4.2.1. Definition of Endpoint

The primary efficacy endpoint is the proportion of subjects who have a recurrence of uveitis in the study eye within 24 weeks (6 months) after receiving study treatment. Recurrence is defined as:

- An increase in the vitreous haze of ≥ 2 steps compared to baseline at the Week 24 visit, or any visit time point prior to the Week 24 visit after the Study Day 7 visit

Or

- A deterioration in visual acuity of at least 15 letters BCVA compared to baseline at the Week 24 visit, or any visit time point prior to the Week 24 visit after the Study Day 7 visit.

Any criterion used to define recurrence must be attributable only to noninfectious uveitis. To prevent post-procedural inflammatory reactions from being reported as uveitis recurrences, assessments for recurrence of uveitis begin after the Study Day 7 visit.

The study protocol stated to impute subjects who don't complete Week 24 eye examinations and subjects who take prohibited medications as having a recurrence. Consider the fact that the study was terminated early, no imputation will be implemented. Summary of the primary efficacy endpoint will be based only on the observed data from the subjects who reached Week 24.

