3 INVESTIGATIONAL PLAN

3.1 Overall Study Design

[figure not shown]
The protocol was originally planned to be a 52-week, prospective, randomized, masked (subject and outcome assessor), controlled, safety and efficacy study of intravitreal Yutiq 0.05 mg compared to sham injection with a primary efficacy and safety readout at 24 weeks.

The Sponsor has decided to stop enrollment for reasons other than safety or efficacy in early May 2022, following FDA advice received on January 24, 2022. The Sponsor is reevaluating the development program of Yutiq 0.05 mg. Subject enrollment has been stopped, and all subjects have been unmasked. Subjects who were randomized to the sham injection were discontinued from the study and underwent their EOS visit. Subjects who were randomized to sham injection may have been treated with standard of care medication, if necessary. Subjects who were randomized to Yutiq 0.05 mg will be followed on a modified protocol schedule through Month 12 (or ET) and evaluated for efficacy and safety.

As depicted in [Figure 3-1](#), subjects will receive either Yutiq 0.05 mg or a sham injection on Day 1 of the study. Subjects who were treated with Yutiq 0.05 mg will be assessed over the following 52 weeks on a modified protocol schedule according to the schedule presented in

Table 5–1. Subjects who were randomized to the sham injection were discontinued from the study and underwent their EOS visit.

Figure 3-1: Study Design Schema, Study EYP-2102-001

Note: The sponsor decided to stop enrollment for reasons other than safety or efficacy in early May 2022, following FDA advice received on January 24, 2022. The Sponsor is reevaluating the development program of Yutiq 0.05 mg. Subject enrollment in the study has been stopped. All subjects who were currently enrolled have been unmasked. Subjects who were to receive Yutiq 0.05 mg will be followed on a modified protocol schedule through Month 12 (or ET).

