11.4.4 Efficacy Analyses

Efficacy analyses will be performed on both the ITT and PP populations at 24 and 52 weeks. The primary efficacy analysis will be performed on the ITT population at 24 weeks and will be the proportion of subjects who have a recurrence of uveitis. The exact 95% CI for the proportion will be derived. Hypothesis testing using the exact binomial test will be conducted to test the

difference between the proportion of subjects with a recurrence using a 2-sided alpha = 0.05. The primary efficacy analysis will be conducted after all subjects in the study have completed at least 24 weeks of study or have discontinued.

In addition to recurrence based on vitreous haze increase or BCVA loss as defined above, recurrence will also be imputed in the following circumstances:

- A subject who has not previously experienced a recurrence and does not complete the required eye examinations at Week 24 (or at Week 52 for the Week 52 analyses) for any reason will be considered as having a recurrence.
- A subject who has not previously experienced a recurrence and takes a prohibited systemic concomitant medication or a prohibited local concomitant medication in the study eye at any time during the study prior to Week 24 (or prior to Week 52 for the Week 52 analyses) will be considered as having a recurrence.

Systemic medications or topical steroids administered as part of gradual dose reduction (tapering) will not be considered prohibited medications. Topical steroids, including those administered as part of short-term standard treatment following an ocular surgical procedure, will also not be considered prohibited medications.

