11.4.5 Use of Rescue and Prohibited Medications

During the study, some subjects may require rescue treatments in the study eye as a result of AEs or lack of efficacy of the study treatment. Prior to database lock, the Sponsor will conduct a blinded data review to classify concomitant treatments as either rescue ([Section 7.6](#)) or prohibited ([Section 7.7](#)). The proportion of subjects receiving these medications will be summarized by treatment type (rescue or prohibited), treatment group, and time point.

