4.4.7.1. Use of Rescue and Prohibited Medications

All prohibited medications used concurrently (from Day 1 through Month 12) must be documented in the eCRF. During the study, some subjects may require rescue treatments in the study eye as a result of AEs or lack of efficacy of the study treatment. Prior to database lock, the Sponsor will conduct a data review to classify concomitant treatments as either rescue or prohibited. The proportion of subjects receiving these medications will be summarized by treatment type (rescue or prohibited), treatment group, and time point.

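### SAP 4.2.1 drops the prohibited-medication recurrence rule for a reason that does not by itself cover subjects who reached Week 24; no planned summary shows the overlap, and SAP 4.8 omits the change

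*SAP*

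**What the plan says.** - **Protocol 11.4.4** (repeated in the Synopsis) imputes recurrence in two circumstances beyond the haze and BCVA criteria. One is failure to complete the Week 24 eye examinations. The other is a subject without an earlier recurrence who "takes a prohibited systemic concomitant medication or a prohibited local concomitant medication in the study eye at any time during the study", if this falls before Week 24. Both rules have a Week 52 counterpart. Tapering and certain topical steroid use are exempt.
- **SAP 4.2.1** acknowledges both rules and then says: "Consider the fact that the study was terminated early, no imputation will be implemented". It sets the denominator as follows: "Summary of the primary efficacy endpoint will be based only on the observed data from the subjects who reached Week 24". SAP 4.3.1.1 carries the same definition to Week 52.
- **SAP 4.1.1** makes all summaries descriptive and based on observed data, also because of early termination. SAP 4.2.3 plans no sensitivity analysis.
- **SAP 4.4.7.1** confirms that the data exist: "All prohibited medications used concurrently (from Day 1 through Month 12) must be documented in the eCRF". It plans the proportion of users by type (rescue or prohibited), arm and time point. As part of SAP 4.4 this is a safety-set summary.
- **SAP 4.8** lists two departures from the protocol: no hypothesis test, and redefined analysis populations.

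**The concern.** The two rules do different work, yet one reason is given for removing both. The sponsor discontinued the sham subjects, so counting every missed Week 24 examination as a recurrence would measure the sponsor's decision and not the disease. Dropping that rule is well explained.

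The medication rule concerns recorded events in subjects who may have stayed to Week 24. For them, early termination is not in itself a reason to ignore non-exempt steroid or immunosuppressant use. One possible case is systemic therapy taken at entry that runs past the three-month limit of Protocol 7.2, if it is then no longer classed as taper.

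With no test planned, the proportion and its interval are the whole primary result. A reader of that table cannot tell how many subjects counted as recurrence-free were on such treatment.

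**Working it through.** The plan gives no recurrence rate, enrolled number or power figure, so there is nothing of its own to reproduce. The check is one of text, plus arithmetic for scale.

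**1. Can the planned tables reveal the overlap?** Let k be the subjects with haze/BCVA recurrence, p the prohibited-medication users and n the subjects in the arm. Even on one common denominator, the two separate proportions only bound the count with the rule kept:

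max(k, p) ≤ count ≤ min(k + p, n).

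Illustration (k and p assumed): n=30, k=6, p=3 gives between 6 and 9, that is 20.0% to 30.0%. If p=0 the bounds meet at k and the effect is shown to be zero. In the SAP the denominators also differ: safety set for medication use, subjects reaching Week 24 for recurrence.

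**2. Size of the effect.** Let x be the haze/BCVA recurrences among n subjects reaching Week 24, and m those who qualify by medication only. The main rate is x/n and the supplementary rate is (x+m)/n, so the difference is 100·m/n points. It is never negative, and it is zero when m=0.

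The 95% Clopper-Pearson limits for x of n are the Beta quantiles B(0.025; x, n−x+1) and B(0.975; x+1, n−x).

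Inputs: n=30 is the planned arm size (SAP 1.2). The values n=20 and n=10, the 20% base rate and m=1 are assumptions.

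| n | Main row | With m=1 | Difference |
|---|---|---|---|
| 30 | 6/30 = 20.0% (7.7–38.6) | 7/30 = 23.3% (9.9–42.3) | 3.3 |
| 20 | 4/20 = 20.0% (5.7–43.7) | 5/20 = 25.0% (8.7–49.1) | 5.0 |
| 10 | 2/10 = 20.0% (2.5–55.6) | 3/10 = 30.0% (6.7–65.2) | 10.0 |

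**3. When would the supplementary estimate leave the main row's own interval?** Find the smallest m for which (x+m)/n exceeds the main row's upper limit.

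- 20% base: n=30, m=6 (12/30 = 40.0% > 38.6%); n=20, m=5 (9/20 = 45.0% > 43.7%); n=10, m=4 (6/10 = 60.0% > 55.6%).
- No haze/BCVA events: the upper limits are 11.6%, 16.8% and 30.8% at n=30, 20 and 10. In each case m=4 is needed (13.3%, 20.0%, 40.0%).

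One affected subject therefore leaves the intervals overlapping almost entirely.

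**The case against.** The strongest reply is that the drop follows a consistent policy. Protocol 11.4.4 itself calls the medication rule imputation, and SAP 4.1.1 confines everything to observed data because the trial stopped. This stands in part: it explains why the SAP treated the two rules alike. It does not settle the matter, because prohibited use is itself an observed, dated record.

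There is also a stop-related reason that the SAP could have given. Protocol 3.1 reports: "Subject enrollment has been stopped, and all subjects have been unmasked". Protocol 11.4.5 still says that "the Sponsor will conduct a blinded data review to classify concomitant treatments as either rescue" or prohibited, whereas SAP 4.4.7.1 says only that "the Sponsor will conduct a data review to classify concomitant treatments as either rescue or prohibited". Unmasked classification is a fair ground for caution about the rule, but the SAP does not state it.

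Four stronger readings are tempting, and the documents do not support them:

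- **That the change is hidden.** SAP 4.2.1 states it openly beside the endpoint definition. The gap in 4.8 is one of listing.
- **That the SAP rate is the worse estimate.** Protocol 10.1 requires recurrence to be attributable only to noninfectious uveitis, and some prohibited use may have other indications.
- **That the effect cannot be found at all.** Zero prohibited use would show in the 4.4.7.1 table, and by-subject listings are planned.
- **That Protocol section 11 has been breached.** It lets the SAP modify the plan and asks for an amendment only for major changes to the primary endpoint or its analysis. Nothing shows that this one is major.

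**Conclusion.** The point holds as a minor one. For subjects who reached Week 24, the stated reason does not by itself account for dropping the medication rule. The overlap between non-exempt use and recurrence-free status is in no planned summary unless prohibited use is zero, and SAP 4.8 is incomplete.

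For given data, the SAP rate can only equal or fall below the rate with medication use counted, by 100/n points per affected subject. Both m and the true n are unknown, m may be zero, and sham n may be very small or zero after the discontinuation in early May 2022. No test depends on the rate.

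**What to change.** 1. Keep the haze/BCVA rate as the main row.
2. Among subjects reaching Week 24 (and likewise Week 52), add one supplementary descriptive row per arm with a Clopper-Pearson interval. It also counts use, before that time point, of non-exempt steroids or systemic immunosuppressants named in Protocol 7.7, with local use counted in the study eye only. Label it as narrower than the full protocol rule, since 7.7 also covers therapies that would have barred entry.
3. Split the medication-only subjects by recorded indication (uveitis or other).
4. Cross-tabulate recurrence status against rescue and prohibited use. Rescue under Protocol 7.6 is exempt, so it would not appear in the supplementary row.
5. Because subjects are unmasked, define the flag in the SAP by drug class, route, eye and date. Identify use dated after the sponsor's stop; for the sham arm Protocol 3.1 notes: "Subjects who were randomized to sham injection may have been treated with standard of care medication, if necessary".
6. Before producing the row, reconcile Protocol 7.7 with 11.4.4 on topical steroids. Section 7.7 lists them as not permitted, with exceptions for tapering, rescue and short-term use after ocular surgery. Section 11.4.4 reads as exempting topical steroids more generally.
7. Add the change to SAP 4.8, with a separate reason for the medication rule.

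No new data are needed: SAP 6.2.6 shows that drug, route, dates and indication are collected. The cost is SAP wording, the reconciliation, a little table and classification work, and a row that may include non-uveitis use, which the indication split makes visible.

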Major Protocol Violation: There was failure to meet the protocol entry criteria or the subject failed to adhere to the protocol requirements or received prohibited medication (eg, subject failure to follow instructions, or inability to complete study assessments). The violation necessitated premature termination from the study.

Other: The subject was terminated for a reason other than those listed above, such as termination of study by the Sponsor or a regulatory authority. The Investigator must specify the reason.

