1.2. Study Design

The protocol was originally planned to be a 52-week, prospective, randomized, masked (subject and outcome assessor), controlled, safety and efficacy study of intravitreal Yutiq 0.05 mg compared to sham injection with a primary efficacy and safety readout at 24 weeks. A total of approximately 60 subjects (30 subjects in the Yutiq 0.05 mg group and 30 in the sham treatment group) were to be enrolled at approximately 40 sites in the US. One eye in each subject will be designated as the study eye.

The Sponsor decided to stop enrollment in early May 2022 for reasons other than safety or efficacy, following FDA advice received on January 24, 2022. Subjects who were randomized to Yutiq 0.05 mg will continue to be monitored on a modified-protocol schedule through Month 12 (or ET) and evaluated for efficacy and safety. Those subjects who had been treated with sham injection were discontinued from the study and subsequently had their End of Study (EOS) evaluation.

[figure not shown]
Subjects will receive either Yutiq 0.05 mg or a sham injection on Day 1 of the study on the study eye and will be assessed over the following 52 weeks according to the schedule of study procedures and assessment.

Yutiq 0.05 mg is a non-erodible intravitreal implant in a drug delivery system that contains 0.05 mg of FA and is designed to release FA at a rate of 0.25 µg/day into the vitreous humor for at least 6 months. Yutiq 0.05 mg is preloaded into a single-dose applicator to facilitate injection of the implant directly into the vitreous.

To ensure the health of both eyes, observations of both the study eye and non-study (fellow) eye

should be made at all visits as described in the schedule of study procedures and assessments. Ocular data will be collected for both eyes at all visits except for the SD-OCT assessments.

Figure 1. Study Design Schema

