4.2.3. Sensitivity Analysis

No sensitivity analysis will be performed.

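### The SAP cancels the protocol's recurrence imputation in both arms because of early termination, but only sham follow-up was stopped, so Yutiq subjects without a Month 6 examination leave the primary proportion unseen

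*SAP*

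**What the plan says.** Protocol 11.4.4 adds two imputed routes to recurrence for a subject who has not already had one. The first applies when the subject "does not complete the required eye examinations at Week 24 (or at Week 52 for the Week 52 analyses) for any reason"; the second applies when the subject takes a prohibited systemic medication, or a prohibited local one in the study eye.

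SAP 4.2.1 acknowledges both routes and removes them without naming an arm: "Consider the fact that the study was terminated early, no imputation will be implemented". It then sets the denominator: "Summary of the primary efficacy endpoint will be based only on the observed data from the subjects who reached Week 24". SAP 4.1.3 takes Week 24 assessments from the Month 6 visit. SAP 4.3.1.1 and 4.3.2 carry the same method to Week 52. SAP 4.2.3 closes the matter: "No sensitivity analysis will be performed".

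On who was stopped, Protocol 3.1 says that sham subjects were discontinued and had an end-of-study visit, whereas Yutiq subjects "will be followed on a modified protocol schedule through Month 12 (or ET) and evaluated for efficacy and safety". Protocol 5.1 keeps Months 6 and 12 for them, and SAP 1.2 repeats that their follow-up continues.

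**The concern.** The reason given fits one arm and is applied to two. For sham subjects withdrawn by the sponsor before Month 6, the protocol rule would turn an administrative decision into treatment failures, so dropping it there is right. For Yutiq subjects the visit stayed on the schedule, and a missing examination is the situation that the protocol rule was written for. Early termination also says nothing about prohibited medication in either arm.

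With the sham arm cut short and no hypothesis test, the Yutiq proportion and its exact interval become the main efficacy result. Removing subjects without a Month 6 examination makes it a completers-only figure, although SAP 3.1 names all randomized subjects as the default efficacy set. If missing the visit is related to poor disease control or intolerance, the figure flatters the product.

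**Working it through.** **Plan's own figure.** There is none to reproduce. SAP 1.2 gives a planned size of about 60 (30 per arm), but neither document gives an expected recurrence rate, a loss rate, or the number actually randomized. The point does not depend on the planned size.

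**Inputs.**
- N: subjects randomized to Yutiq (not given)
- k: Yutiq subjects with no prior recurrence and no Month 6 examination (not given)
- x: Yutiq subjects with an observed recurrence, taken here to be all among those who reached Week 24 (not given)
- Interval: Clopper-Pearson 95% (SAP 4.2.2)
- Prohibited-medication use: set to zero here, to isolate the missed-examination route

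**Formulas.**
- SAP 4.2.1: x/(N − k)
- Protocol 11.4.4, missed-examination route: (x + k)/N
- Gap: (x + k)/N − x/(N − k) = k(N − k − x)/[N(N − k)] = (k/N) × [1 − x/(N − k)]

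Since x cannot exceed N − k, the gap is never negative, and it is zero when k = 0. Prohibited-medication users without a recurrence would be added to the protocol-rule numerator, which can only widen it.

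**Illustration.** Assumed: x = 20% of N, and k about 10% or 20% of N.

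| N | k | x | SAP rule (95% CI) | Protocol rule (95% CI) | Gap, points |
|---|---|---|---|---|---|
| 10 | 1 | 2 | 2/9 = 22.2% (2.8-60.0) | 3/10 = 30.0% (6.7-65.2) | 7.8 |
| 15 | 3 | 3 | 3/12 = 25.0% (5.5-57.2) | 6/15 = 40.0% (16.3-67.7) | 15.0 |
| 20 | 2 | 4 | 4/18 = 22.2% (6.4-47.6) | 6/20 = 30.0% (11.9-54.3) | 7.8 |
| 20 | 4 | 4 | 4/16 = 25.0% (7.3-52.4) | 8/20 = 40.0% (19.1-63.9) | 15.0 |
| 30 | 3 | 6 | 6/27 = 22.2% (8.6-42.3) | 9/30 = 30.0% (14.7-49.4) | 7.8 |
| 30 | 6 | 6 | 6/24 = 25.0% (9.8-46.7) | 12/30 = 40.0% (22.7-59.4) | 15.0 |

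Check by the gap formula: 0.10 × (1 − 2/9) = 7.8 points; 0.20 × (1 − 1/4) = 15.0 points. With x = 30% of N = 30, the gap is 40.0 − 33.3 = 6.7 points (k = 3) or 50.0 − 37.5 = 12.5 points (k = 6).

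**A wording point in the same sentence.** SAP 4.2.1 counts a recurrence at any visit after Day 7, yet it restricts the summary to subjects who reached Week 24. Read literally, a Yutiq subject who recurs and then leaves before Month 6 is also dropped. If one of the three recurrences in the N = 15 row were such a case, the SAP figure would be 2/11 = 18.2% (2.3-51.8), while the protocol rule would still give 6/15.

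**The case against.** The case for leaving the plan alone has four parts.

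- **It is disclosed and descriptive.** SAP 4.2.1 states the protocol rule, says that it is dropped and gives a reason. SAP section 1 announces a reduced list of analyses, and SAP 4.1.1 plans no test. This stands and limits the weight of the point: no decision rule hangs on the proportion.
- **The figure can be rebuilt.** SAP 4.4.1 tabulates subjects remaining at each visit, SAP 6.2.1 gives completion and reasons for termination, and SAP 4.1.1 promises by-subject listings. This also stands. What is missing is a planned presentation of the figure, not the data behind it.
- **The stop may have reached the Yutiq arm indirectly.** All subjects were unmasked and the sponsor was reevaluating the programme (Protocol 3.1), so some Yutiq departures may be related to that. A subject may also miss Month 6 and attend Month 12. A missing examination therefore does not show that the subject left, or left for an ordinary clinical reason. This stands, and it is why reasons should be shown beside the row. It does not rescue a blanket waiver: the protocol rule was written to apply whatever the reason, and the text that describes the sham discontinuation still carries it.
- **Counting every missing examination as a recurrence is harsh.** It is a worst-case bound and can move the Yutiq figure in one direction only. That is a reason to make it supportive, not to omit it.

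A reader might also infer that the rule was dropped to improve the result, because SAP version 1.0 is dated 08MAY2023, a year after enrollment stopped and subjects were unmasked. The documents do not show that results influenced the choice, and the point does not rely on it.

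**Conclusion.** The reason and its scope do not match. Early termination justifies waiving the missed-examination rule for sham subjects stopped by the sponsor; it does not by itself justify waiving it for Yutiq subjects, whose visits continued. The direction is fixed by arithmetic: the SAP figure for Yutiq equals or falls below the protocol-rule figure.

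The size is not known. For missed examinations it is zero if every Yutiq subject had a Month 6 examination, and about 8-15 percentage points under the assumed 10-20% loss and 20% observed recurrence. It would be wrong to read that range as the bias in the planned result: it is what follows if every missing subject is called a recurrence, and the intervals in the illustrations overlap widely. Nor is any number stated in the documents shown to be wrong. This is a cheap improvement to a descriptive report, not a flaw that invalidates it.

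**What to change.** Keep the observed-data row as planned, and make these changes to the SAP:

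1. In 4.2.1, limit the early-termination reason to sham subjects whom the sponsor stopped.
2. In 4.2.3, replace "No sensitivity analysis will be performed" with one supportive Yutiq-only row at Week 24 and one at Week 52. All randomized Yutiq subjects form the denominator. Observed recurrences count whenever they occurred after Day 7. A subject with no prior recurrence counts as a recurrence under both Protocol 11.4.4 routes, missed required examination or prohibited medication.
3. Show the reasons for missing examinations beside the row. For subjects who terminated, the termination eCRF described in Protocol 4.4 records them; its category for other reasons covers cases "such as termination of study by the Sponsor or a regulatory authority". State how early-termination examinations are treated, since Protocol 11.3.3 maps them to the next visit and SAP 4.1.3 does no re-mapping.
4. List the dropped imputation and the new row in SAP 4.8, which at present mentions neither.

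The row should not be extended to sham. In an assumed arm of 15 with 10 stopped by the sponsor, 2 other dropouts and 3 completers with 1 recurrence, leaving out the sponsor-stopped subjects and counting the other dropouts as recurrences gives (1 + 2)/(15 − 10) = 3/5 = 60%, against 1/3 = 33% observed. That would flatter Yutiq by comparison.

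The cost is a few sentences and one extra row per time point from data already planned for collection, using the rescue or prohibited classification that SAP 4.4.7.1 already requires before database lock. The treated-arm figure may look less favourable.
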